⁴ Weeks 8 and beyond, collections/assessments may occur ± 5 days from specified time points, except for MRI scans, which can occur ± 7 days on Weeks 12 and 96 and must be performed pre-infusion on infusion days (- 7 days) on Weeks 24 and 48. MRI scan at Early Withdrawal from Treatment Visit should be performed within 4 weeks after withdrawing from the study.

⁵ Prior to each infusion except PT/INR which is completed at baseline. Urine Pregnancy Test on non-infusion days subjects will test upon arrival at the site

⁶ Prior to infusion and 30 minutes +/- 15 minutes post-infusion on infusion days. For non-infusion days, one PK sample should be obtained

⁷ Anti-Drug Antibodies are antibodies developed against ublituximab

⁸ Physical examination will occur on all visits except Week 1 Day 2 and Week 2 Day 8

⁹ Within 2 hours pre-infusion and 60 minutes +/- 15 minutes post-infusion on any infusion day

¹⁰ Re-consent following a suspected relapse is required if the relapse is confirmed by IRAP or by the Treating Neurologist (Treating Neurologist medically confirmed relapse), whichever comes first. Re-consent must occur within 6 weeks after first reporting of relapse. Re-consent may occur at the next schedule office visit but may require an unscheduled visit if the relapse occurs between Weeks 24 and 96 (where the frequency of scheduled visits is every 12 weeks).

¹¹ Serum pregnancy test must be completed within 5 days prior to Week 1 Day 1

¹² Obtain blood sample for teriflunomide drug concentration test prior to first dose of accelerated teriflunomide elimination procedure

¹³ Prior to each infusion

¹⁴ The Unscheduled Relapse Visit will be conducted if a possible relapse is reported by the subject. The visit is to be planned as soon as possible, within 7 days from subject notification of the relapse to the site. Infusion visit is delayed until relapse is back to baseline, or Treating Neurologist/PI does not expect any improvements.

¹⁶ Teriflunomide/oral placebo administration shall be taken in the morning until the last day of Week 95. Alternative dosing times are allowed if necessary.

¹⁷ Sample for teriflunomide concentration to be collected before the first oral dose of teriflunomide/oral placebo

¹⁸ For Unscheduled Relapse Visit, EDSS assessment (by Examining Neurologist) and neurological examination (by Treating Neurologist) will be performed independently

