6.1 OVERVIEW

All subjects should visit the study center on the days specified within this protocol. The complete schedule of assessments is shown in Section 6 (Tables 5, 6, and 7) and Appendix F. The screening physical examination with vital signs, medical history, evaluation of concomitant medications, EDSS (fatigue will not contribute to the EDSS score), complete blood count/full blood count (3 part differential accepted), serum chemistry, and a baseline ECG should be done within 28 days prior to initiation of treatment. For women of child bearing potential, a serum pregnancy test should be completed within 5 days prior to Week 1 Day 1. MRI scans should be performed ≤ 28 days prior to initiation of treatment.

Week 1/Day 1 EDSS must be assessed within 1 day prior to randomization (i.e., on the day before randomization or on the day of randomization but before randomization occurs) and must be documented.

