6.3.3 RADIOLOGICAL EVALUATION

Magnetic Resonance Imaging (MRI) is a useful tool for monitoring CNS lesions in MS. Different MRI derived parameters have been related to clinical activity and T1 weighted gadolinium-enhancing lesions or new and/or enlarging hyperintense T2 lesions have been related to relapses. It is hypothesized that changes in brain volume may reflect brain atrophy as a result of MS-related tissue loss and may thereby correlate with long-term clinical outcomes in RMS subjects.

Brain MRI scans will be obtained in all subjects as detailed in the Schedule of Assessments in Section 6. In addition, brain MRI scans will be obtained in subjects who had withdrawn from the trial. Scans will be performed by trained and certified MRI technicians.

Assessment of effect on Gd enhancing lesion and new, enlarging T2 lesions, brain volume, T1 hypointense will be evaluated as outlined in the schedule of events by a central reader. The following time windows apply:

- “Baseline” MRI should be performed after informed consent is obtained, but preferably 10 days prior to the Week 1 Day 1 visit.
- MRI are scheduled as follows: Weeks 12 (+/- 7 days), 24 (pre-dose; - 7 days), 48 (pre-dose; - 7 days) and 96 (+/- 7 days)
- MRI scans may be performed on the day of withdrawal or within 4 weeks after withdrawing from the study.
 - The MRI may not be needed if an MRI was obtained within 30 days prior to withdrawal from the trial.

If subjects receive corticosteroids for a relapse, every effort should be made to obtain the scan prior to the first steroid dose if the pre-steroid scan is within 1 week of the scheduled visit. In subjects receiving corticosteroids, there should be an interval of at least 30 days between the last dose of corticosteroids and the scan.

At each time point, the MRI will include acquisition of scans with and without intravenously administered gadolinium contrast enhancement.

MRI scans will be read by a centralized reading center located in Montreal, Canada for efficacy endpoints. The centralized reading center is blinded to the treatment assignment and the reading is performed in the absence of clinical information. Additional details on scanning acquisition sequences, methods, handling and transmission of the scans, certification of site MRI radiologists/technicians, and the procedure for the blinded analysis of the scans at the central reading center will be described in a separate MRI Manual.

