6.9 RE-SCREENING PROCEDURES

Subjects may be re-screened under the following conditions:

- After a relapse recovery (see Section 4.4.1) and upon re-consent
- Varicella titer does not indicate immunity at initial screening and subject is re-immunized (see Section 3.2)
- He/she, at initial screening, is not eligible to participate in the study based on inclusion/exclusion criteria (Sections 3.1 and 3.2) and wishes to re-assess eligibility after a waiting period deemed sufficient by the site investigator.
- The subject was determined eligible, but 28 days or more has elapsed between the initial screen and the first infusion (Week 1 Day 1).

Re-screening procedures are identical to initial screening procedures (Appendix F), but with the following modifications:

- Medical history does not need to be taken again.
- Screening MRI may not need to be repeated if there was one obtained within 30 days prior to this screening

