### 2.1.3 Efficacy Variables

Evaluation schedule for efficacy variables are presented in TG1101-RMS302 protocol.

Baseline is defined as the last non-missing value on or before the date of randomization. For subjects who have no value on or before randomization date, the last non-missing value on or before the date of first dose will be used as baseline. Baseline MRIs delayed due to scheduling problems or re-testing, a window of up to 30 days will be allowed for use of the baseline MRI value.

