### 2.4.3.2 MRI

The following MRI results will be provided by the central lab:

Measurement/Visit	SCREENING	WEEK 12 DAY 84	WEEK 24 DAY 168	WEEK 48 DAY 336	WEEK 96 DAY 672	EARLY WITHDRAWAL FROM TREATMENT
T1 Unenhancing Lesion Count	X					
T2 Lesion Count	X					
New Enlarging T2 Lesion Count			X (Screening)	X (Previous)	X (Previous)	X (Previous)
New Enlarging T2 Lesion Volume			X (Screening)	X (Previous)	X (Previous)	X (Previous)
T2 Lesion Volume	X		X	X	X	X
New T1 Unenhancing Lesion Count			X (Screening)	X (Previous)	X (Previous)	X (Previous)
T1 Unenhancing Lesion Volume	X		X	X	X	X
Normalized Brain Volume	X					
Brain Volume			X	X	X	X
Gad Enhancing Lesion Count	X	X	X	X	X	X

Gad Enhancing Lesion Volume	X		X	X	X	X
-----------------------------	---	--	---	---	---	---

The analysis endpoints will be derived as follows:

Protocol endpoint	MRI test result to be used	Derivation
total number of gadolinium enhancing (Gd-enhancing) T1-lesions per MRI scan by Week 96	Gad Enhancing Lesion Count (GADCNT)	$[GADCNT(w12)+GADCNT(w24)+GADCNT(w48)+GADCNT(w96)]/[number\ of\ MRIs\ available\ (w12/w24/w48/w96)]$ Note: the division by the number of MRIs will be accomplished by an offset in the negative binomial regression
Total number of new and enlarging T2 hyperintense lesions (NELs) per MRI scan by Week 96	New Enlarging T2 Lesion Count (NEWT2CNT)	$[NEWT2CNT(w24)+\ NEWT2CNT(w48)+\ NEWT2CNT(w96)]/[number\ of\ MRIs\ available\ (w24/w48/w96)]$ Note: the division by the number of MRIs will be accomplished by an offset in the negative binomial regression
Volume of hypointense T1 lesion component (black holes)	T1 Unenhancing Lesion Volume (T1UNVOL)	T1UNVOL (w24) , T1UNVOL (w48) ,T1UNVOL (w96)
Volume of T2 lesion	T2 Lesion Volume (T2VOL)	T2VOL(w24), T2VOL(w48),T2VOL(w96)
MRI part of NEDA definition (no T1 Gd+ lesions and no new/enlarging T2 lesions)	Gad Enhancing Lesion Count (GADCNT), New Enlarging T2 Lesion Count (NEWT2CNT)	All values , GADCNT(w24), GADCNT(w48), GADCNT(w96), NEWT2CNT(w24), NEWT2CNT(w48), NEWT2CNT(w96) need to be zero
Percent change in brain volume as detected by MRI compare to baseline	Brain Volume (BV)	$(BV(w24) - NBV(baseline))/NBV(baseline)*100$ $(BV(w48) - NBV(baseline))/NBV(baseline)*100$ $(BV(w96) - NBV(baseline))/NBV(baseline)*100$
Total volume of Gd-enhancing T1 lesions per MRI scan over the treatment period	Gad Enhancing Lesion Volume (GADVOL)	$[Sum\ of\ all\ post-baseline\ GADVOL(w24/w48/w96)]/[number\ of\ MRIs\ available\ (w24/w48/w96)]$

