#### 2.4.3.3 NEDA

The proportion of subjects with no evidence of disease activity (NEDA) will be calculated at Week 96. A subject with NEDA is defined as a subject without evidence of disease activity, which is defined as a subject without relapses confirmed by the IRAP, without MRI activities (no T1 Gd+ lesions and no new/enlarging T2 lesions), and no 12-week Confirmed Disability Progression.

1. Any evidence of disease activity from Week 24 to Week 96 will be counted as not reaching NEDA. Any evidence of disease activity before Week 24 will not count.
2. In the case of early termination at any time point (including before Week 24), even if an event was not reported before early discontinuation, the subject will be considered as not reaching NEDA.

NEDA rates will be compared using logistic regression [REDACTED] with baseline adjustments the same as used in the primary endpoint analysis, without treatment duration offset, but including log-transformed baseline MRI counts (T1 unenhancing, T2, Gad enhancing).

To avoid zero values for the log transformation of MRI counts, 1 will be added to each observation before transforming.

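### The NEDA derivation fails subjects on a Week 24 T2 count that covers almost only the period before Week 24, which both documents exclude from the endpoint

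*SAP*

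**What the plan says.** Protocol 8.9.2 and SAP 2.4.3.3 define NEDA over Week 24 to Week 96, and both state: "Any evidence of disease activity before Week 24 will not count". SAP 2.4.3.3 adds that a subject who terminates early, at any time, is counted as not reaching NEDA.

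The derivation table in SAP 2.4.3.2 turns the MRI part of that definition into counts. For T2 it states: "NEWT2CNT(w24), NEWT2CNT(w48), NEWT2CNT(w96) need to be zero". It asks the same of the gadolinium counts at Weeks 24, 48 and 96. The row for the first key secondary endpoint sums "GADCNT(w12)+GADCNT(w24)+GADCNT(w48)+GADCNT(w96"), so the Week 12 gadolinium count is used there and left out of NEDA.

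The central-lab table in the same section gives the reference scan for each new/enlarging T2 count. The Week 24 count is marked as read against Screening. The Week 48, Week 96 and early-withdrawal counts are marked as read against the previous scan. No T2 count is delivered at Week 12.

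On timing, footnote 4 to the schedule in Protocol Section 6 says that scans "must be performed pre-infusion on infusion days (- 7 days) on Weeks 24 and 48". Protocol 6.3.3 gives the same window: "24 (pre-dose; - 7 days), 48 (pre-dose; - 7 days"). For the screening scan, Protocol 6.1 says: "MRI scans should be performed ≤ 28 days prior to initiation of treatment".

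**The concern.** A count read against Screening on a pre-infusion Week 24 scan can contain only lesions that appeared or enlarged before that scan. Requiring it to be zero brings into NEDA the T2 activity that the definition leaves out. The SAP then holds two rules for one endpoint, and they can classify the same subject differently.

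NEDA is fourth in the hierarchy of SAP 2.4.3.1, tested at 0.05, and it gates the SDMT and brain volume endpoints. If the conflict is still open at unblinding, someone will have to choose between two written definitions of a confirmatory endpoint with the results within reach.

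**Working it through.** The plan gives no NEDA rate, T2 lesion rate or power for NEDA, so there is no figure of its own to reproduce. The check is date arithmetic and a comparison of the rules.

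**Inputs.** Screening scan Day -28 to Day 0 (Protocol 6.1 and Table 5). Week 24 = Day 168 and Week 96 = Day 672 (Tables 6 and 7). Week 24 scan 0 to 7 days before, so nominally Day 161 to 168. Week 96 is held at Day 672.

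**1. Interval covered by the Week 24 T2 count** = scan day minus screening day.
- Shortest: 161 - 0 = 161 days.
- Longest: 168 + 28 = 196 days.
- Days after Day 168: none, on the nominal schedule.

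**2. Whole T2 component as derived, against the stated window.**
- Stated: 672 - 168 = 504 days.
- Derived: 672 - 0 = 672 days, up to 672 + 28 = 700 days.
- Ratio: 672/504 = 1.33 to 700/504 = 1.39.
- Share before Week 24: 168/672 = 25% to 196/700 = 28%.

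**3. Visit window.** Footnote 4 also allows visits ±5 days. If the 7-day scan window follows the actual infusion visit, the scan can fall from 168 - 5 - 7 = Day 156 to 168 + 5 = Day 173. At most 5 days of the interval then lie after Day 168; with a screening scan on Day 0 that is 5/173 = 2.9%. An infusion visit postponed for a suspected relapse (Protocol 5.2) can move the scan later still.

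**4. One subject under both rules.** Only activity: one new T2 lesion in Week 6; completes Week 96.

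| Rule | Result |
|---|---|
| Protocol 8.9.2 and SAP 2.4.3.3 | NEDA: the lesion is before Week 24 |
| SAP 2.4.3.2, NEDA row | Not NEDA: the Week 24 count is at least 1 |

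**5. What the exclusion would do for T2 if the table governs.** The first scheduled T2 read is at Week 24. The only read that could come earlier is at early withdrawal, and those subjects already fail. The exclusion would therefore remove no T2 activity in any other subject.

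**6. Effect on the comparison.** In each arm, keeping the term can only lower the NEDA proportion or leave it unchanged. For the contrast, take assumed rates that are not in the documents: 60% v 45% without the term, 220 per arm, two-sided 0.05, power 0.886.
- 30% of those subjects reclassified in both arms: 0.60 × 0.70 = 42.0% v 0.45 × 0.70 = 31.5%; power 0.628.
- 30% v 50% reclassified: 42.0% v 0.45 × 0.50 = 22.5%; power 0.993.

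The direction depends on rates that the documents do not give.

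**7. Time before Week 24 that remains once the term is dropped.** The T2 interval then starts at the Week 24 scan.
- From Day 161: 672 - 161 = 511 days, of which 7/511 = 1.4% is before Week 24.
- From Day 156: 672 - 156 = 516 days, of which 12/516 = 2.3%.
- More where the Week 24 scan is invalid and the Week 48 count goes back to an earlier scan.

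**The case against.** The strongest defence is that the exclusion speaks of evidence, not of lesion onset. Evidence of a new T2 lesion first exists when the scan shows it, and SAP 2.5.2 ties scans to nominal visits. On that view a Week 24 scan belongs to the window, and dropping the Week 12 gadolinium count shows that the authors applied the Week 24 start by visit. The table is also explicit, applies equally to both arms and uses a blinded central read.

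Part of this stands. The rule can be programmed as written, and no bias or type I error inflation has been shown. Keeping the Week 24 gadolinium count, which comes from the same pre-infusion scan, does rest on the nominal-visit convention, so the SAP should say so. That count is a reading at one time point, however; it does not accumulate from Screening.

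The defence does not remove the conflict. Neither document states that reading for NEDA. Assigning a scan to a visit does not change the interval that a Screening-referenced count covers. As step 5 shows, the exclusion would then be empty for T2.

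A reader might infer that the Week 24 scan can never fall after Week 24, or that the fix leaves at most 7 days of earlier activity. The documents do not support either. The ±5-day visit window, postponed infusion visits, the 30-day gap after corticosteroids (Protocol 6.3.3) and the exclusion of invalid scans (SAP 2.4.3.2) all loosen those limits.

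**Conclusion.** The conflict is real and confined to the T2 component of NEDA. As derived, that component spans about 672 to 700 days against a stated 504, with 25% to 28% of it before Week 24. These are shares of calendar time on the nominal schedule, not effects on NEDA.

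Longer or shorter spans are tempting but not secure. Protocol 6.9 says: "Screening MRI may not need to be repeated if there was one obtained within 30 days prior to this screening". Adding 28 + 30 = 58 days would give 672 + 58 = 730 days, but Protocol 6.1 and Appendix F still place the scan within 28 days of first treatment. SAP 2.1.3 says that "a window of up to 30 days will be allowed for use of the baseline MRI value" without naming the date from which it runs. The figure of 672 - 30 = 642 days needs the assumption that it runs forward from the start of treatment.

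A reader might also infer that the rule favours one arm, or that the NEDA test is invalid. The documents show neither the size nor the direction of any effect on the contrast. The primary endpoint and the first three key secondary endpoints are untouched. This is a should-fix before lock: two written definitions of an alpha-controlled endpoint that a small edit can reconcile.

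**What to change.** Before database lock and unblinding:

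1. Remove the Week 24 new/enlarging T2 count from the NEDA row of SAP 2.4.3.2. Require zero at Week 48 (read against Week 24) and at Week 96 (read against Week 48).
2. Keep the gadolinium counts at Weeks 24, 48 and 96, and state that for NEDA they are taken by nominal visit. State also that the T2 interval starts at the Week 24 scan, so that T2 activity between Day 168 and a late scan is knowingly left out of the T2 component.
3. Add a rule for subjects with no valid Week 24 T2 scan, whose previous scan at Week 48 may be Screening. One option is to count a nonzero Week 48 value as not NEDA and to flag these subjects. Without a rule, activity before Week 24 can re-enter here.
4. Report NEDA under the present table rule as a sensitivity analysis.

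Cost: one term removed, one rule and a clarifying sentence or two added, one extra table and the matching programming. No new scans or reads are needed, because the Week 48 and Week 96 counts are already delivered. The small remainder shown in step 7 of the working should be acknowledged.

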 - Blood collection for B lymphocyte cell counts (% CD19+ B cells) at screening, and Week 1 Day 1 (pre-dose), Week 1 Day 2, Week 2, Week 3 Day 15 (pre-dose), and Weeks 4, 8, 12, 16, 20, 24 (pre-dose), 48 (pre-dose), and 72 (pre-dose), 84 and 96 (or Early Withdrawal from Treatment), 100 and 104. Also, at any Unscheduled Relapse Visits.

MRI Schedule: Screening, Weeks 12, 24 (pre-dose) and 48 (pre-dose) and 96

Clinical Assessment Schedule: Screening, Week 1 Day 1 (pre-dose) Weeks 12, 24 (pre-dose), 36, 48 (pre-dose), 60, 72 (pre-dose), 84 and 96

For further information on the scheduled events for each study visit see Tables 5, 6 and 7 in Section 6 and Appendix F.

Screening Lab Evaluation (Central Lab)

- CBC with differential
- Varicella titer
- Serology to rule out active Hep B/C and HIV
- Serum chemistry
- Serum pregnancy test
- B lymphocyte cell counts (% CD19+ B cells)
- See Section 6 for complete listing of laboratory assessments

ADA Assessment:	All subjects will have six serum samples taken to assess for the presence of ADA prior to the infusions on Week 1 Day 1, Week 3 Day 15 and Weeks 24, 48, and 72. In addition, a serum sample will be taken at Week 96.																																	
Pharmacokinetic (PK):	
Serum samples will be drawn from all subjects pre-infusion on infusion days of ublituximab or IV placebo and at 30 minutes +/- 15 minutes post-infusion on infusion days (Week 1 Day 1, Week 3 Day 15, Weeks 24, 48, and 72). One additional serum sample will be taken on Week 96.
 
Only serum samples from subjects treated with ublituximab will be analyzed for serum ublituximab concentrations. See the Laboratory Manual for PK collection and processing instructions.
																																	
Plasma Concentration for Teriflunomide	
In order to assess teriflunomide compliance, four plasma samples will be taken from all subjects. The first sample will be taken prior to oral administration of teriflunomide or oral placebo on Week 1 Day 1. The second sample will be taken prior to infusion of ublituximab or IV placebo on Week 48. The third sample will be taken Week 96. The last plasma sample for teriflunomide will be taken at Week 116.
 
Only plasma samples from subjects treated with teriflunomide will be analyzed for plasma teriflunomide concentrations. See the Laboratory Manual for PK collection and processing instructions.
																																	

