8.9.2 SECONDARY EFFICACY VARIABLES

The key secondary outcomes will be tested using a hierarchical approach with the order specified below using a step-down procedure where each test is at a Type I error 0.05. If any endpoints fail to reach significance, then formal testing of significance of the subsequent secondary outcomes will not be performed.

1. Total number of gadolinium enhancing (Gd-enhancing) T1-lesions per MRI scan by Week 96.
2. Total number of new and enlarging T2 hyperintense lesions (NELs) per MRI scan by Week 96.
3. Time to Confirmed Disability Progression (CDP) for at least 12 weeks occurring during the 96-week, double-blind treatment period. *
4. Proportion of subjects with No Evidence of Disease Activity (NEDA) from Week 24 to Week 96.
5. Proportion of subjects reaching impaired SDMT (Symbol Digit Modalities Test) from baseline to Week 96.
6. Percentage change in Brain Volume from baseline to Week 96.

* Confirmed Disability Progression for at least 12 weeks during the 96-week treatment period will be analyzed using pooled data from the two identical studies TG1101-RMS301 and TG1101-RMS302.

The total number of gadolinium enhancing (Gd-enhancing) T1-lesions will be calculated as the sum of the individual number of lesions at weeks 12, 24, 48, and 96, divided by the total number of MRI scans of the brain. The total number of new and enlarging T2 hyperintense lesions will be calculated as the sum of the individual number of lesions at weeks 24, 48, and 96, divided by the total number of MRI scans of the brain. The MRI count variables will be assessed for differences between the treatment groups using negative binomial regression with an offset based on time on study and covariates, region, baseline EDSS strata, and baseline MRI counts. Percent brain volume change will be assessed between the two groups using linear mixed effects models [REDACTED] with covariates region, baseline EDSS strata, and baseline brain volume.

Disability progression is defined as an increase of ≥ 1.0 point from the baseline EDSS score that is not attributable to another etiology (e.g., fever, concurrent illness, or concomitant medication) when the baseline score is 5.5 or less, and ≥ 0.5 when the baseline score is above 5.5. Disability progression is considered confirmed when the increase in the EDSS score is confirmed at regularly scheduled visits at least 12 or 24 weeks after the initial documentation of neurological worsening.

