MRI data will only be used for analysis if not rejected or invalid, e.g. due to change of scanner, indicated as comments from the central lab.

MRIs will also be excluded from analysis if corticosteroids (ATC level 2 = “CORTICOSTEROIDS FOR SYSTEMIC USE”) were dosed within 30 days prior to the scan.

The MRI count variables (Total Number of gadolinium enhancing (Gd-enhancing) T1-lesions per MRI scan at Weeks 12 (where applicable), 24, 48, and 96, Total number of new and enlarging T2 hyperintense lesions (NELs) per MRI scan at Weeks 24, 48, and 96) will be assessed for differences between the treatment groups using negative binomial regression with an offset based on the log-transformed number of post-baseline MRI scans and covariates region, baseline EDSS strata, and corresponding baseline lesion count.

For analysis of percent brain volume change from baseline, a Mixed Model Repeated Measures (MMRM) analysis will be implemented via [REDACTED] by fitting percent change from baseline values on the cube root transformed volume from all visits after baseline in the treatment period with scheduled assessments of brain volume. The models will include factors (fixed effects) for treatment, region, baseline EDSS strata, visit, treatment-by-visit interaction, and baseline value of

the brain volume (cubic root transformed). The factor, visit, with nominal visits to avoid undue reliance on a linear in time effect will have 3 levels (Week 24, Week 48 and Week 96). An unstructured correlation matrix will be used to model the within-patient errors. Parameters will be estimated using restricted maximum likelihood method with the Newton-Raphson algorithm. Denominator degrees of freedom will be estimated using Satterthwaite's approximation.

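### Protocol 8.9.2 models both MRI lesion counts with a time-on-study offset, which contradicts its own per-scan definitions and the SAP's scan-count offset

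*SAP*

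**What the plan says.** Protocol 8.9.2 gives this definition for Gd lesions: "sum of the individual number of lesions at weeks 12, 24, 48, and 96, divided by the total number of MRI scans of the brain"; and this one for T2 lesions: "sum of the individual number of lesions at weeks 24, 48, and 96, divided by the total number of MRI scans of the brain". That same paragraph then says that both counts are analysed by "negative binomial regression with an offset based on time on study and covariates, region, baseline EDSS strata, and baseline MRI counts".

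SAP 2.4.3.2 has the same two per-scan definitions. Its derivation table lists Weeks 12, 24, 48 and 96 for Gd and Weeks 24, 48 and 96 for T2, and notes in each row that "the division by the number of MRIs will be accomplished by an offset in the negative binomial regression". The model paragraph below the table fits both counts "using negative binomial regression with an offset based on the log-transformed number of post-baseline MRI scans".

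Three further facts matter. The synopsis gives "MRI Schedule: Screening, Weeks 12, 24 (pre-dose) and 48 (pre-dose) and 96". The SAP's table of central readings shows new or enlarging T2 lesions read against screening at Week 24 and against the previous scan at Weeks 48 and 96, while Gd lesions have no reference scan. The SAP also says that "MRIs will also be excluded from analysis if corticosteroids" for systemic use were given in the 30 days before the scan.

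**The concern.** An offset fixes what a count is a rate of. The protocol states one denominator in the endpoint definition (scans) and another in the model (time), and the SAP, written for that protocol version and carrying the same date, states a third position by using scans throughout. These are different models for key secondary tests 1 and 2. Under SAP 2.4.3.1 both must be significant in both studies before the pooled 12-week disability progression test is confirmatory, and that test in turn opens endpoints 4 to 6. If the conflict is left open, the offset for two gatekeeping tests could be settled after the results are known.

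**Working it through.** Neither document gives a power, rate or event figure for the MRI counts, so there is no planned figure to reproduce. The check has four steps.

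**1. Gd lesions under the protocol's time offset.** Inputs: scans at Weeks 12, 24, 48 and 96. Section 8.9.2 does not define time on study, so I take it as running to the last scan. With the same Gd count per scan, the implied rate relative to a completer is (completer's weeks per scan) / (subject's weeks per scan).

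| Last scan | Scans | Weeks per scan | Implied rate vs completer |
|---|---|---|---|
| Week 12 | 1 | 12/1 = 12 | 24/12 = 2.0 |
| Week 24 | 2 | 24/2 = 12 | 24/12 = 2.0 |
| Week 48 | 3 | 48/3 = 16 | 24/16 = 1.5 |
| Week 96 | 4 | 96/4 = 24 | 1.0 |

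The factor shrinks if the subject stays on study after the last scan. It can also go the other way: a completer with one scan excluded has 96/3 = 32 weeks per scan, so 24/32 = 0.75.

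**2. T2 lesions under the SAP's scan offset.** Inputs: intervals of 24, 24 and 48 weeks from the table of central readings; constant accrual is an assumption. The expected count per scan is proportional to weeks covered per scan.

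| Scans available | Weeks per scan | vs completer |
|---|---|---|
| All three | 96/3 = 32 | 1.0 |
| Last at Week 24 or 48 | 24/1 or 48/2 = 24 | 0.75 |
| Week 48 excluded but still the Week 96 reference | (24+48)/2 = 36 | 1.125 |
| Week 48 missing, Week 96 read against Week 24 | (24+72)/2 = 48 | 1.5 |

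The SAP does not say which of the last two rows applies.

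**3. Effect between arms.** The documents mention 10% dropout without a split by arm, so the splits here are assumptions, as is a last scan at Week 24 for every dropout. First, as a ratio of totals with 5% dropout on ublituximab and 15% on teriflunomide:

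- Weeks: 0.95×96 + 0.05×24 = 92.4 against 0.85×96 + 0.15×24 = 85.2.
- Gd scans: 0.95×4 + 0.05×2 = 3.9 against 0.85×4 + 0.15×2 = 3.7. Time-offset distortion: (3.9/92.4)/(3.7/85.2) = 0.972.
- T2 scans: 0.95×3 + 0.05×1 = 2.90 against 0.85×3 + 0.15×1 = 2.70. Scan-offset distortion: (92.4/2.90)/(85.2/2.70) = 1.010.

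A fitted negative binomial model does not weight subjects as a ratio of totals does, so it was also simulated: 300 replicates, 220 per arm, treatment-only model, true rate ratio 0.50, dispersion 2, T2 mean 1.5 per 32 weeks, Gd mean 0.5 per scan (all assumed except 220).

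| Dropout, ublituximab/teriflunomide | Gd, time offset | Gd, scan offset | T2, scan offset | T2, time offset |
|---|---|---|---|---|
| 0%/0% | 0.496 | 0.496 | 0.496 | 0.496 |
| 10%/10% | 0.491 | 0.498 | 0.503 | 0.502 |
| 5%/15% | 0.467 | 0.502 | 0.512 | 0.500 |
| 5%/25% | 0.438 | 0.501 | 0.523 | 0.499 |

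On the same simulated data, the scan-to-time ratio for Gd is 1.074 at 5%/15% and 1.146 at 5%/25%. For T2 it is 1.024 and 1.049.

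**4. Is a time offset clean for T2?** Only if lesions accrue steadily. Suppose a share f of a ublituximab completer's T2 lesions is seen by Week 24, teriflunomide accrues evenly (share 0.25), and 10% drop out of each arm after Week 24. The ratio of totals is multiplied by (0.9 + 0.1f)/(0.9 + 0.1×0.25). For f = 0.5 this is 0.950/0.925 = 1.027; for f = 0.95 it is 0.995/0.925 = 1.076. The factor is the same under either offset.

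**The case against.** The strongest reply is that a working rule already exists. Protocol Section 8 defers full details to the SAP, and the SAP says that it was revised before database lock to cover the technical aspects of the analysis. With complete scans the offset is constant and the treatment ratio is identical either way. This limits the consequence but does not remove the conflict: deferring detail is not the same as stating a contrary model, and neither document says which prevails.

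A reader might infer the stronger claim that the SAP's scan offset is wrong for T2 and that time is the right denominator. The documents do not support that. Both define the T2 endpoint per MRI scan, and the SAP's offset is exactly that division, with a T2-specific list of scans. A rate over time would be a different estimand. It would also need steady accrual, which neither document states, and step 4 shows that front-loaded lesions distort both offsets equally. The first interval is not exactly 24 weeks either, because protocol 6.1 allows the baseline scan up to 28 days before treatment. What remains valid for T2 is narrower: the per-scan value depends on which scans are available.

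**Conclusion.** The protocol's time-on-study offset should not stand. It contradicts the protocol's own definition of both endpoints and the SAP's model, and it is unsuitable for Gd lesions, where it can double the implied rate of an early dropout. Under the assumed 5%/15% dropout it moved the simulated Gd ratio from 0.502 to 0.467, in favour of ublituximab. The direction is not fixed: it reverses if ublituximab has more dropout, and scans lost to steroid treatment of relapses push the other way.

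The SAP's T2 offset is correct for the endpoint as defined. Its sensitivity to scan pattern is worth about 1-5% on the ratio under the assumed unequal dropout, against ublituximab when teriflunomide loses more subjects. It vanishes with complete scans. All between-arm sizes rest on assumed dropout splits and, for T2, on constant accrual. It would overstate the case to say that the two documents must give different results.

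**What to change.** Before unblinding:

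- In protocol 8.9.2, replace the time-on-study offset with the SAP's endpoint-specific one: for Gd, the log of the number of evaluable scans among Weeks 12, 24, 48 and 96; for T2, the log of the number among Weeks 24, 48 and 96. Repeat the two lists in the SAP's model paragraph, whose general reference to post-baseline scans could be read as counting Week 12 for T2.
- Add a T2 sensitivity analysis whose offset is the log of the time actually covered by the intervals whose lesions enter the sum. Time from baseline to the last evaluable scan would not do. If an excluded Week 48 scan remains the Week 96 reference, the lesions cover 24 + 48 = 72 weeks against an offset of 96, which understates that subject's rate by 25%. An early-withdrawal scan could likewise extend the offset, although its lesions are outside the sum.
- State which scan is the Week 96 reference when Week 48 is missing or excluded.

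The cost is a few sentences and one extra analysis. No new data are needed.
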